## 2.8 Reasons for exclusion from the analyses

Any major protocol deviation will be described and its impact on inclusion in each analysis population for any subject will be specified. The final list of protocol deviations impacting each analysis population will be reviewed prior to interim analysis and database lock. The list may be updated, up to the point of interim analysis and database lock, to include any additional major protocol deviations impacting inclusion in each analysis population.

## 3 STATISTICAL METHODS

### 3.1 Statistical analysis strategy

The statistical analyses will be performed in accordance with ICH E9 guideline and will be based on the pooled data from the individual study sites, unless otherwise stated.

Statistical analyses will be performed by **CC1** managed by the sponsor's biometry department.

Data from phase I and phase II will be analysed and reported separately. Phase I analyses will be performed by cohort and in total for the applicable population. Phase II analyses will be performed by cancer type for efficacy analyses and by cancer type and in total for safety analyses for the applicable population.

#### 3.1.1 Primary endpoints

##### Phase I

The primary endpoint is the MTCA or the MACA if the MTCA is not identified during the phase I. The primary variables determining the MTCA will be the incidence of DLTs and the cumulative organ absorbed doses (Gy) during two cycles of treatment. The DLT assessment

period for the determination of the primary endpoint starts from the first administration of  $^{177}\text{Lu}$ -OPS201 and ends 6 weeks after the second administration.

The MTCA is defined as the maximum cumulative radioactivity that may be administered following fractionated i.v. administrations of at least 6 weeks apart, so that:

- no more than 33% of the subjects experience a DLT after first or second administration of  $^{177}\text{Lu}$ -OPS201 and/or
- no more than 10% of the subjects have cumulative absorbed dose in each target organ exceeding the acceptability limits (1.5 Gy in BM and 23 Gy in kidney) after second administration of  $^{177}\text{Lu}$ -OPS201.

The MTSA is defined as the highest single radioactivity that can be given so that no more than 33% of the subjects experience a DLT during Cycle 1. The MTSA will be determined in case of unacceptable toxicity seen after first administration of  $^{177}\text{Lu}$ -OPS201.

The MACA will be determined if the MTCA is not reached during the dose escalation.

## **Phase II**

Phase II primary endpoint is to evaluate the ORR of fractionated i.v. administration of  $^{177}\text{Lu}$ -OPS201 in previously treated subjects with locally advanced or metastatic cancers expressing sstr2 as identified by  $^{68}\text{Ga}$ -OPS202 PET/CT scans. The primary endpoint is ORR measure by RECIST 1.1 over the two treatment cycles of the core study. Objective response is defined as the sum of PR and CR measured by CT or MRI using RECIST version 1.1. Tumour response assessments are performed 6 weeks after each administration of  $^{177}\text{Lu}$ -OPS201 during the core study or at the time of occurrence of first clinical signs of disease progression as determined by the investigator. All images will be sent to an ICL for evaluation and confirmation of response.

### ***3.1.2 Secondary endpoints***

All imaging endpoints will be assessed by blinded independent readers managed by the ICL.

## **Phase I**

### ***Pharmacokinetics, biodistribution and dosimetry***

For PK, biodistribution and dosimetry of  $^{177}\text{Lu}$ -OPS201, the endpoints are:

- $C_{\max}$ ,  $t_{\max}$ , maximal uptake (%), AUC at the target lesions, discernible organs and blood and elimination half-life ( $t_{1/2}$ ) of radioactivity concentrations in blood.
- Highest absorbed dose, Specific absorbed dose to the target lesions (Gy/GBq), Specific absorbed dose per organ (Gy/GBq) and Cumulative absorbed organ doses (Gy).

For PK of OPS201, the endpoints are:

- Pharmacokinetic parameters including, but not limited to,  $C_{\max}$ , AUC,  $t_{1/2}$ , total plasma clearance (CL), apparent volume of distribution ( $V_d$ ), cumulative amount (of unchanged drug) excreted into the urine ( $A_e$ ), renal clearance, as measured in plasma and urine at defined timepoints.

### ***Pharmacodynamic/efficacy***

- Mean change (%) in tumour volume at 6 weeks after each  $^{177}\text{Lu}$ -OPS201 administration compared to Screening as assessed by CT or MRI:
  - RECIST version 1.1 (tumour size is defined as the sum of the diameters of the target lesion in subjects who received  $^{177}\text{Lu}$ -OPS201)
  - volumetric CT
- PFS as determined from start of study treatment until occurrence of tumour progression or death.

SAP Final: Version 2.0: [03 January 2020]

31/57

- BOR defined as the best response recorded from the start of the treatment until disease progression/recurrence.
- ORR defined as proportion of subjects with a BOR characterised as either CR or PR relative to the total number of evaluable subjects.
- DCR defined as proportion of subjects with a BOR characterised as CR, PR or stable disease relative to the total number of evaluable subjects.
- PFS will be evaluated as defined per RECIST version 1.1.
- OS at 1-year and 2-year follow-up as determined from start of study treatment until occurrence of death of any cause.
- Quantitative changes (SUV normalised by lean body mass ( $SUL_{max}$  and  $SUL_{mean}$ ) in tumour-to-background  $^{18}F$ -FDG-PET uptake using PERCIST version 1.0, from Screening to 6 weeks after second  $^{177}Lu$ -OPS201 administration (second cycle).
- Changes in tumour uptake (assessed based on  $SUV_{max}$  and  $SUV_{mean}$ ) on  $^{68}Ga$ -OPS202 PET/CT from Screening to 6 weeks after second  $^{177}Lu$ -OPS201 administration (second cycle) as compared to clinical response and BOR.
- Correlation between change (%) in tumour uptake on  $^{68}Ga$ -OPS202 PET/CT (assessed based on  $SUV_{max}$  and  $SUV_{mean}$ ) at screening with tumour response to  $^{177}Lu$ -OPS201 therapy from Screening to 6 weeks after second  $^{177}Lu$ -OPS201 administration (second cycle) using ceCT/MRI – RECIST v1.1.
- Correlation between the uptake of  $^{68}Ga$ -OPS202 in tumour lesions expressing sstr2 on PET/CT images and the uptake on  $^{177}Lu$ -OPS201 SPECT/CT.
- Diagnostic sensitivity of  $^{68}Ga$ -OPS202 imaging using RECIST by subject-based analysis.
- Diagnostic sensitivity of  $^{68}Ga$ -OPS202 imaging using mGa-RECIST by subject-based analysis.
- Diagnostic sensitivity of  $^{68}Ga$ -OPS202 imaging by subject-based, organ-based and lesion-based analysis compared to standard-of-truth (SOT) of ceCT (or ceMRI).
- Diagnostic sensitivity of  $^{68}Ga$ -OPS202 imaging by both organ-based and lesion-based analysis compared to standard-of-truth (SOT) of  $^{177}Lu$ -OPS201 SPECT/CT.

## **Phase II**

### **Efficacy**

- Durable response rate (DRR: CR or PR lasting  $\geq 6$  months)
- Progression free survival (PFS) as determined from start of study treatment until occurrence of tumour progression or death. Progression will be radiologically assessed by RECIST v1.1 and “mGa-RECIST” as two separate endpoints; for RECIST it will be measured at Screening and 6 weeks after each  $^{177}Lu$ -OPS201 administration (each cycle); for “mGa-RECIST” it will be measured at Screening and 6 weeks after the second  $^{177}Lu$ -OPS201 administration (second cycle).

PFS (months) = (event or censoring date – first dose date + 1)/30.4375

PFS will be right-censored for subjects who met one or more of the following conditions:

- no baseline disease assessment or no evaluable post baseline disease assessments unless death occurred prior to the first planned assessment at post baseline (in which case death will be considered a PFS event).

SAP Final: Version 2.0: [03 January 2020]

32/57

- amputation or surgical resection of tumour in the absence of documented disease progression.
- subsequent anticancer therapy in the absence of documented disease progression.
- died or documented disease progression after missing two or more consecutively scheduled disease assessment visits
- alive and without documented disease progression on or before the data cutoff date

If a subject meets more than one of these conditions, then the scenario that occurs first will be used for analysis. The progression or censoring date will be determined based on the conventions listed in Table 4:

Table 4 Date of Progression or Censoring for PFS

Situation	Date of progression or censoring	Outcome
Death before first planned disease assessment	Date of death	Event
Death or disease progression between planned disease assessments	Date of death or first disease assessment showing disease progression, whichever occurs first	Event
No baseline disease assessment or no evaluable post-baseline disease assessments	Date of first dose of  Lu-OPS201	Censored
Surgical resection or subsequent anticancer treatment started before disease progression or death (without disease progression beforehand)	Date of last disease assessment prior to surgery or start of subsequent anticancer treatment	Censored
Death or disease progression after missing two or more consecutively scheduled disease assessments	Date of last disease assessment visit without documentation of disease progression before the first missed visit	Censored
Alive and without disease progression	Date of last disease assessment	Censored

- Other response endpoints (same timepoints as for PFS):
  - disease control rate (DCR)
  - time to progression (TTP)
  - time to response (TTR)
  - duration of response (DoR)

TTP or TTR (months) = (event or censoring date – first dose date + 1)/30.4375

TTP does not include deaths. Deaths are censored, either at the time of death or at an earlier visit representing informative censoring.

The progression or censoring date will be determined based on the conventions listed in Table 5:

**Table 5 Date of Progression or Censoring for TTP**

Situation	Date of progression or censoring	Outcome
Death before or after first planned disease assessment	Date of death	Censored
Disease progression between planned disease assessments	Date of first disease assessment showing disease progression	Event
No baseline disease assessment or no evaluable post-baseline disease assessments	Date of first dose of  Lu-OPS201	Censored
Surgical resection or subsequent anticancer treatment started before disease progression (without disease progression beforehand)	Date of last disease assessment prior to surgery or start of subsequent anticancer treatment	Censored
Disease progression after missing two or more consecutively scheduled disease assessments	Date of last disease assessment visit without documentation of disease progression before the first missed visit	Censored
Alive and without disease progression	Date of last disease assessment	Censored

DOR will be calculated as follows for subjects who have a BOR of CR or PR:

DOR (months) = (Event/Censoring Date – Response Start Date + 1) / 30.4375

Subjects who meet one or more of the following conditions will be right-censored for DOR:

- amputation or surgical resection of tumour in the absence of documented disease progression.
- subsequent anticancer therapy in the absence of documented disease progression
- died or documented disease progression after missing two or more consecutively scheduled disease assessment visits
- alive and without documented disease progression on or before the data cut-off date

If a subject meets more than one of these conditions, then the scenario that occurs first will be used for the analysis. The progression or censoring date will be determined based on the conventions listed in Table 6.

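### Table 5 keeps a subject who stops being scanned at risk for time to progression until death, with no missed-visit rule for deaths as in Tables 4 and 6, and this can only raise the TTP curve

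*SAP*

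**What the plan says.** All references are to the SAP, section 3.1.2, Phase II, unless stated otherwise.

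- **Text above Table 5.** TTP does not count deaths as events: "Deaths are censored, either at the time of death or at an earlier visit representing informative censoring". It does not say when the earlier visit applies. The next sentence makes the table govern: "The progression or censoring date will be determined based on the conventions listed in Table 5".
- **Table 5, death row.** "Death before or after first planned disease assessment": censored at the date of death, with no condition.
- **Table 5, missed-visit row.** "Disease progression after missing two or more consecutively scheduled disease assessments": censored at the last assessment before the gap. Deaths are not mentioned.
- **Table 5, other rows.** "Alive and without disease progression": censored at the last disease assessment. "No baseline disease assessment or no evaluable post-baseline disease assessments": censored at first dose. Surgery or new anticancer treatment before progression: censored at the last assessment before that intervention.
- **Tables 4 (PFS) and 6 (duration of response).** The matching row reads "Death or disease progression after missing two or more consecutively scheduled disease assessments", so deaths are included and go back to the last assessment before the first missed visit.
- **Precedence.** For PFS and duration of response, the scenario that occurs first is used when several apply. No such sentence is given for TTP.
- **Estimator and population.** Section 3.2.1.1 analyses TTP as PFS is analysed, by Kaplan-Meier. Section 2.2.2 assigns TTP to the per-protocol (PP) population, which requires at least one post-baseline response assessment. Section 3.2.1.1 names both ITT and PP for tumour response.

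**The concern.** Progression is observed only on scans. Between the last scan and death a subject cannot have a TTP event, yet under Table 5 that subject stays in the risk set for the whole interval. A living subject in the same position leaves the risk set at the last scan, as does one found to have progressed after two missed assessments. Only the subject who dies is carried forward.

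Two things follow. The same subject can have longer follow-up for TTP than for PFS, and the TTP curve is inflated by subjects who were not being observed. In addition, the table and the sentence above it do not agree, and some deaths fit two rows with different dates, so two programmers could derive different TTP datasets from the same SAP.

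**Working it through.** The SAP gives no TTP figure (no median, event count or assumed rate), so there is nothing to reproduce. The check has three parts.

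**1. One subject under each rule.** Scans are taken at weeks 6 and 12 and then every 3 months. The first two follow from the six-week cycles. The 3-monthly scans are an assumption: section 1.2 gives follow-up visits at intervals of 3 (unit missing, read as months) to 24 months, and Table 2 lists only screening and 6 weeks after each administration. Week 12 is 84/30.4375 = 2.76 months, so the next scans fall at 5.76 and 8.76 months (ignoring the one-day offset in the formula). Suppose the last scan is at 2.76, the next two are missed, and the subject dies at month 10 (illustrative):

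| What happens | Rule | Censored at (months) |
|---|---|---|
| Death, TTP | Table 5, death row | 10 |
| Same death, PFS | Table 4, missed-visit row | 2.76 |
| Progression found after the same gap, TTP | Table 5, missed-visit row | 2.76 |
| Alive, no progression, TTP | Table 5, alive row | 2.76 |

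**2. Direction.** The Kaplan-Meier estimate is the product over event times of 1 − d/n, with d progressions and n at risk. Deaths are censored under either rule, so d is the same. Table 5 gives n + c, where c is the number of subjects between their last scan and their death. Since 1 − d/(n + c) ≥ 1 − d/n at every event time, the Table 5 curve can never lie below the curve with earlier censoring.

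**3. Size, by simulation.** None of the inputs below is in the SAP except the sample sizes.

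*Scenario set A.* n = 76 and 96 (planned enrolment, section 1.3.4); latent median TTP 3 months (SCLC-like) and 5 months (BC-like); median time to death before progression 12 and 24 months; median survival after progression 4 and 10 months. At each visit 5%, 10% or 15% permanently stop scanning. Deaths are still recorded, and no one who stops scanning starts new treatment. Progression-free share at month 6:

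| Set | Table 5, at 5/10/15% stopping | Deaths censored at last scan | Excess (points) |
|---|---|---|---|
| SCLC-like, PP | 33/36/39% | 29–30% | about 3/6/9 |
| BC-like, PP | 48/51/52% | about 46% | about 2, 4–5, 6 |
| SCLC-like, never-scanned kept | 36/42/48% | about 30% | 6/12/18 |
| BC-like, never-scanned kept | 50/55/58% | about 46% | 4, 8–9, 12 |

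A repeat with 400 replicates gave PP excesses of 3.3/6.2/9.5 and 2.1/4.2/6.4 points. Applying the Table 4/6 missed-visit rule to deaths brought the share to 31–32% and about 47%, which removes most of the excess. With no missed scans the difference is zero. If half of those who stop scanning start new treatment, and the new-treatment row is taken to apply, the PP excess falls to about 1.5/3/5 and 1/2/3.5 points. If all do, it is zero. The SCLC-like median did not move. The BC-like median moved by one scan interval (5.76 to 8.76 months), and in PP only at the higher stopping rates.

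*Scenario set B.* n = 69 and 87 (response evaluable, section 1.3.4); median TTP 4 and 6 months; median time to unrelated death 24 months; 10% to 40% of subjects stop after one to three scans; median 4 or 8 months from last scan to death. Table 5 against the Table 4/6 rule:

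| | Mildest case | Most severe case |
|---|---|---|
| n = 69, month 6 | 37.8 − 36.8 = 1.0 | 43.4 − 38.1 = 5.3 |
| n = 69, month 9 | 23.2 − 21.8 = 1.4 | 32.5 − 24.0 = 8.5 |
| n = 87, month 6 | 52.3 − 51.5 = 0.8 | 56.8 − 52.4 = 4.4 |
| n = 87, month 9 | 38.1 − 36.8 = 1.3 | 45.2 − 37.1 = 8.1 |

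The typical median was unchanged throughout (5.76 and 8.76 months), because events fall only on scan dates.

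**The case against.** The strongest reply is that the SAP does not fix a single rule for every death. The sentence above Table 5 allows an earlier visit, and a death after surgery or new treatment also meets a row dated at the prior assessment. This stands. The defect is partly an unconditional row and partly an unresolved conflict, but the conflict does not rescue the rule, because the text hands the decision to Table 5 and its death row has no earlier-visit option.

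The second reply concerns size. A reader might infer a large distortion, up to 18 points at month 6. That figure keeps subjects with no post-baseline scan and carries them to death. The PP population assigned to TTP requires a post-baseline assessment, and another Table 5 row would date such subjects at first dose. In PP the effect is roughly halved, and it shrinks further if those who stop scanning move to other treatment, which is plausible in these cancers. This stands too.

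Third, TTP is secondary and descriptive, with no test or decision attached. Section 5 limits the report, after premature closure, to selected listings, none of them TTP. A reader might infer that a reported result is too long; the document does not support that.

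Last, it is tempting to move every TTP death back to the last scan so as to match PFS. Table 4 contains no such rule: it counts a death between planned assessments as an event and re-dates only deaths after two or more missed assessments.

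**Conclusion.** The point holds as a minor correction. Table 5 omits the missed-visit treatment of deaths that Tables 4 and 6 contain, disagrees with the sentence above it, and leaves overlapping rows without an order of precedence. The direction is certain and needs no assumptions: following Table 5 can only raise the TTP curve relative to earlier censoring.

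The size is conditional. In PP, with 5% to 15% stopping scans per visit, deaths still captured and no new treatment among those who stop, the excess at month 6 is about 3 to 9 points (SCLC-like) or 2 to 6 points (BC-like). It is zero with complete scanning, and the median often stays where it is. The SAP gives no stopping rate, so no single figure can be defended. Under section 5 as it stands, no planned output is affected.

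**What to change.** Four wording changes in SAP section 3.1.2:

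1. Widen the Table 5 missed-visit row to the form used in Tables 4 and 6, "Death or disease progression after missing two or more consecutively scheduled disease assessments", censored at the last assessment before the first missed visit.
2. Limit the Table 5 death row to deaths without such a gap, still censored at the date of death.
3. Reword the sentence above Table 5 so that the earlier visit applies in exactly the situations the table lists.
4. Add to TTP the rule already given for PFS and duration of response, that the scenario occurring first is used. State that a subject with no evaluable post-baseline assessment is censored at first dose, even if the subject later dies.

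The cost is SAP wording only, with no new data and no design change. TTP would come out somewhat shorter if it is ever analysed.

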### *1.3.2.10 Withdrawal/discontinuation*

In accordance with the Declaration of Helsinki (in accordance with the applicable country's acceptance), each subject is free to withdraw from the study at any time. The investigator also has the right to withdraw a subject from the study in the event of concurrent illness, AEs, or other reasons concerning the health or wellbeing of the subject, or in the case of lack of cooperation.

A subject (or a legal representative) has the right to withdraw from the study at any time and for any reason without prejudice to their future medical care by the investigator at the institution.

The investigator and/or sponsor can decide to withdraw a subject from investigational product and/or other protocol-required therapies, protocol procedures, or the study as a whole at any time prior to study completion for the following reasons:

- Subject no longer experiences clinical benefit as determined by the investigator. If study treatment is withdrawn for this reason, the date this decision is to be recorded and every

effort should be made to continue safety evaluations, tumour assessments, and collection of subsequent anticancer treatment information and follow-up information for survival.

- The investigator feels it is not in the best interest of the subject to continue on study.
- Subject participation in another clinical study using an investigational agent or investigational medical device.
- Necessity for treatment with other systemic anticancer therapy (non-protocol defined).
- Necessity for withholding study drug for greater than 6 weeks for study-treatment related AEs.
- Refusal of sexually active fertile subjects (excluding subjects who have been sterilised) to use medically accepted methods of contraception.
- Female subjects who become pregnant.
- Request by the sponsor.
- Subject request to discontinue study treatment (with or without concurrent withdrawal of informed consent).
- Significant noncompliance with the protocol schedule in the opinion of the investigator or the sponsor
- Unacceptable side effects the investigator feels may be due to study treatment.

In addition, if any of the following occur, no further treatment will be administered:

- Cumulative kidney absorbed dose exceeds 23 Gy.
- Cumulative BM absorbed dose exceeds 1.5 Gy during core trial or up to 2 Gy during additional cycles, as determined by dosimetry of peripheral blood samples and imaging.

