**Table 6 Date of Progression or Censoring for DOR**

Situation	Date of progression or censoring	Outcome
Death or disease progression between planned disease assessments	Date of death or first disease assessment showing disease progression, whichever occurs first	Event
Surgical resection or subsequent anticancer treatment started before disease progression or death (without disease progression beforehand)	Date of last disease assessment prior to surgery or start of subsequent anticancer treatment	Censored
Death or disease progression after missing two or more consecutively scheduled disease assessments	Date of last disease assessment visit without documentation of disease progression before the first missed visit	Censored
Alive and without disease progression	Date of last disease assessment	Censored

- Mean change (%) in tumour volume at 6 weeks after each  $^{177}\text{Lu}$ -OPS201 administration (each cycle) compared to baseline, as assessed by volumetric CT/MRI.
- OS at 1-year and 2-year follow-up as determined from start of study treatment until occurrence of death of any cause. Subjects who were lost to follow-up or who were still alive at the time of analysis will be censored at the last day the subject was known to be alive or data cut-off date, whichever occurs first. OS will be calculated as follows:
  - OS (months) = (Death or Censoring Date – First Dose Date + 1)/30.4375
  - Quantitative changes (SUV normalised by lean body mass ( $\text{SUL}_{\text{max}}$  and  $\text{SUL}_{\text{mean}}$ ) in tumour-to-background  $^{18}\text{F}$ -FDG-PET uptake using PERCIST version 1.0, from Screening to 6 weeks after second  $^{177}\text{Lu}$ -OPS201 administration (second cycle).
  - Change in  $^{68}\text{Ga}$ -OPS202 uptake on PET scan after the second  $^{177}\text{Lu}$ -OPS201 administration (second cycle) as assessed by  $\text{SUV}_{\text{max}}$  and  $\text{SUV}_{\text{mean}}$  in subjects screened for  $^{177}\text{Lu}$ -OPS201 treatment as compared to clinical response and ORR.
  - Correlation between tumour uptake on  $^{68}\text{Ga}$ -OPS202 PET/CT (assessed based on  $\text{SUV}_{\text{max}}$  and  $\text{SUV}_{\text{mean}}$ ) at screening with tumour response to  $^{177}\text{Lu}$ -OPS201 therapy from Screening to 6 weeks after second  $^{177}\text{Lu}$ -OPS201 administration (second cycle).

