## **Phase II**

- ORR over the two treatment cycles of the core study measured by the ICL. Objective response is defined as the sum of PR and CR measured by CT or MRI using RECIST version 1.1. Tumour response assessments are performed 6 weeks after each administration of Lu-OPS201 during the core study or at the time of occurrence of first clinical signs of disease progression as determined by the investigator. The point estimates of the ORR will be calculated and accompanied by a 95% exact binomial confidence interval (CI) using the Clopper-Pearson method. ORR by Ga-OPS202 PET mGa-RECIST, will also be analysed similarly. ORR of CMR and PMR by PERCIST 1.0 and by mGa-PERCIST will be analysed similarly as ORR by RECIST 1.1.
- The summaries of BOR will include number and percentage of subjects in each of these categories (CR, PR, SD, PD, NE, NA). BOR will be assessed based on RECIST v1.1 ([Eisenhauer EA, 2009](#)). BOR by Ga-OPS202 mGa-RECIST will also be analysed similarly. BOR by F-FDG-PET PERCIST v1.0 and by mGa-PERCIST will be analysed similarly as BOR by RECIST 1.1 using each of these categories (CMR, PMR, SMD, PMD, NE, NA).
- DRR by RECIST v1.1 defined as the percentage of subjects who have achieved a response of CR, PR or stable disease, will be analysed and summarised in the same manner as ORR.
- PFS by RECIST v1.1 will be summarised descriptively using the Kaplan-Meier method. The Kaplan-Meier estimates of the median PFS, and the corresponding 2-sided 95% confidence intervals calculated using Greenwood's formula will be presented.

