- OS is defined as the time from the date of first dose of  $^{177}\text{Lu}$ -OPS201 to the date of death due to any cause. Subjects who have not died will be censored at the date of last contact which may be identified from a visit date or any study assessment (physical examination, vital signs, ECOG performance status, ECG, study drug record, radiological evaluation, laboratory sampling, concomitant or follow-up procedures), AE, medication, or disposition information. OS will be calculated using the Kaplan-Meier method. One-year and two-year survival are defined as the subject survival probability at 1 year and 2 years, respectively, after the date of first dose of  $^{177}\text{Lu}$ -OPS201. One-year and two-year survival probability along with the associated 2-sided 95% confidence intervals, will be provided. If there are a sufficient number of OS events (i.e., deaths), median OS time, first and third quartiles and associated 95% 2-sided confidence intervals, will be estimated using the Brookmeyer-Crowley method ([Brookmeyer, 1982](#)). Kaplan-Meier OS curves also will be provided.
- DCR by RECIST v1.1, defined as the percentage of subjects who have achieved a response of CR, PR or stable disease, will be analysed and summarised in the same manner as ORR.
- TTP by RECIST v1.1, defined as the time from date of first dose of  $^{177}\text{Lu}$ -OPS201 to the date of first documentation disease progression as determined by the investigator, will be analysed and summarised in the same manner as PFS.
- TTR by RECIST v1.1, defined as the time from the date of first dose of  $^{177}\text{Lu}$ -OPS201 to the date of the first documentation of a response (CR or PR whichever occurs first) in a subject who responded, will be analysed and summarised in the same manner as PFS.
- DoR by RECIST v1.1, defined as the time from date of first documentation of response (CR or PR whichever occurs first) to the date of disease progression or to death due to any cause, whichever occurs first, will be analysed and summarised in the same manner as PFS.

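### Phase II: BOR does not end at tumour resection or new anticancer therapy but DoR is censored before it, so a response first seen afterwards counts and has a negative duration

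*SAP*

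**What the plan says.** **BOR.** The only window the SAP states is in the Phase I list of 3.1.2: "BOR defined as the best response recorded from the start of the treatment until disease progression/recurrence". The Phase II text in 3.2.1.1 gives the BOR categories and the criteria, but no other window. Appendix 1 item 16 deals with missing tumour assessments and adds no cut at surgery or new therapy.

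**ORR, Phase II (3.2.1.1).** It is limited in time: "ORR over the two treatment cycles of the core study measured by the ICL".

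**DoR, Phase II.**
- Subject set (3.1.2): "DOR will be calculated as follows for subjects who have a BOR of CR or PR".
- Formula (3.1.2): "DOR (months) = (Event/Censoring Date – Response Start Date + 1) / 30.4375".
- Start (3.2.1.1): "defined as the time from date of first documentation of response (CR or PR whichever occurs first").
- Censoring when resection or subsequent treatment comes before progression (Table 6): "Date of last disease assessment prior to surgery or start of subsequent anticancer treatment".

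Tables 4 and 5 apply the same cut to PFS and TTP.

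**Scans after study treatment.** Section 1.3.2.10 says, for subjects withdrawn because they no longer benefit, that every "effort should be made to continue safety evaluations, tumour assessments, and collection of subsequent anticancer treatment information and follow-up information for survival". In section 1.2 (Post-treatment Period), follow-up ends at 24 months, progression, death or withdrawal of full consent. The start of another therapy does not end it.

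**The concern.** PFS, TTP and DoR all disregard scans taken after resection or a new anticancer therapy. BOR, which decides who is a responder and who enters the DoR analysis, does not. A subject whose first CR or PR appears after such an intervention, without earlier progression, is thus a responder whose DoR clock starts after its own censoring date.

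Two things follow. A response that may belong to another treatment is credited to the study drug in BOR and TTR. And DoR takes an impossible value that the SAP does not say how to handle, so someone would have to decide after seeing the data whether to drop or alter it. In BOR the error can only be favourable to the study drug.

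**Working it through.** **Inputs.** The DoR, PFS and TTR formulas are from 3.1.2, with first dose as day 1 and no day 0 (Appendix 1 item 8). Core scans fall 6 weeks after each administration, so with administrations 6 weeks apart they fall on days 43 and 85. The denominators, 69 (SCLC) and 87 (BC) response-evaluable subjects, are from 1.3.4. The other dates below are illustrative.

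**The plan's own figures.** The SAP gives no DoR figure to reproduce. The early-termination probabilities in 3.2.16 do reproduce by exact binomial: P(X ≤ 7 | n = 29, p = 0.23) = 0.6555 and P(X ≤ 4 | n = 33, p = 0.12) = 0.6374. Nothing here alters them.

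**Record A: response after the core study.** SD on days 43 and 85, new systemic therapy on day 100, PR on day 150, no progression.
- BOR = PR, since the window is still open on day 150.
- TTR = (150 - 1 + 1)/30.4375 = 4.93 months, counted as an event.
- PFS is censored on day 85: (85 - 1 + 1)/30.4375 = 2.79 months.
- DoR = (85 - 150 + 1)/30.4375 = -64/30.4375 = -2.10 months.
- ORR is unchanged, because day 150 lies outside the two core cycles.

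**Record B: intervention between the two core scans.** SD on day 43, then new therapy or resection, then PR on day 85.
- DoR = (43 - 85 + 1)/30.4375 = -41/30.4375 = -1.35 months.
- The PR falls inside the core window and nothing in the ORR text removes it. Each such subject adds 1/69 = 1.4 points (SCLC) or 1/87 = 1.1 points (BC).

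**When DoR is negative.** With C the last scan before the intervention and S the first response scan, DoR is below zero whenever S - C is 2 days or more. At the planned scan spacing that holds for every first response seen after the intervention. A response that starts before it is unaffected: PR on day 43, last scan on day 85, then new therapy gives (85 - 43 + 1)/30.4375 = +1.41 months.

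**DCR and DRR.** Both records already count for DCR through the earlier SD. DCR changes only for a subject with no evaluable non-PD scan before the new therapy. DRR as defined in 3.1.2 needs a response of at least 6 months, which a negative duration cannot reach.

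**The case against.** The strongest reply is that few subjects can be affected and that nothing in the current report depends on it.

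- **Late scans are not routine.** RECIST timepoints are tied to administrations, and Appendix 1 item 16 works by cycle. The request to continue tumour assessments is attached to one withdrawal reason, loss of clinical benefit. Section 1.2 describes follow-up visits, not scans. This narrows the route but does not close it: the objectives carry PFS into long-term follow-up, and Tables 4 to 6 themselves provide for new therapy before progression.
- **The per-protocol set may remove such subjects.** It excludes major deviations that could affect efficacy (2.2.2), with the list reviewed before interim analysis and lock (2.8). This is a partial safeguard. No rule says that later therapy is such a deviation, and the ITT set keeps these subjects.
- **Section 5 limits the current report to listings after premature closure, none of them a response output.** This stands and lowers the importance of the point. It does not correct the rules in 3.1.2 and 3.2.1.1.

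Some stronger readings are tempting, but the SAP does not support them. A reader might infer that every such subject inflates the primary ORR, but Record A does not touch it. A reader might infer that all BOR-based rates rise, but DCR and DRR behave as shown above. A reader might carry the point to a Phase I cohort of 3 to 5, where one subject is 20 to 33 points. But DoR is not a Phase I endpoint (Table 1), Phase I ORR is also limited to the core cycles, and Phase I response evaluability requires two administrations and reaching the end of Cycle 2 or EOCT. Finally, a reader might infer a definite rise in the type I error of the Simon test, but that needs a frequency the SAP does not give.

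**Conclusion.** The point holds for Phase II as a contradiction between written rules: responder status is read from a longer period than the one in which DoR may be censored. A first CR or PR documented after resection or subsequent anticancer therapy, without earlier progression, enters BOR and TTR as a study response and produces a negative DoR (-2.10 and -1.35 months in the two records). The primary ORR is exposed only through interventions before the last core scan, at 1.4 points (SCLC) or 1.1 points (BC) per subject.

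This assumes that Table 6 is applied as written and that the BOR window in the Phase I list also serves Phase II, where no other is given. The number of subjects concerned is unknown. With that, and with no response output in the current report, the severity is minor.

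**What to change.** In 3.1.2 and 3.2.1.1, define BOR as the best ICL-assessed response from first dose until the earliest of documented progression, tumour resection or start of subsequent anticancer therapy. Treat a scan on the day of the intervention the same way as Table 6 does. Use this window for ORR, DCR, DRR, TTR and the DoR subject set. Any counted response scan is then itself a scan before the intervention, so the Table 6 censoring date for surgery or new therapy cannot precede the response start, and the shortest DoR under that rule is 1 day (1/30.4375 = 0.03 months).

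The cost is one sentence and one programming condition, using dates that Tables 4 to 6 already need. Response counts in BOR or ORR may be slightly lower. The Simon design figures do not change.
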